## **V. INCOMPLETE DISCLOSURE OR DECEPTION**

**a. Incomplete Disclosure/Deception:** Not applicable; participants will be provided with all necessary information before participating in this study.

## **VI. RISKS TO PARTICIPANTS**

**a. Risks:** To our knowledge, there are no anticipated risks to participating in this study. The research makes no claim of providing treatment for mental illness (which will be made clear to individuals prior to participating). Rather, the research team is interested in improving the psychological wellbeing of teens with elevated levels of perceived stress and rumination. Both parents and teens will be required to check a box that indicates they understand this study does not provide treatment for any condition and is not a substitute for medication or therapy. Since this study uses the internet, there's a possibility that someone could see the participants computer or phone screen and see the information they are sending us. Each participant may choose to answer the surveys in a private room or behind closed doors, to protect their privacy.

## **VII. BENEFITS TO PARTICIPANTS**

**a.** By participating in this study, participants will gain access to an online program that may benefit them. We cannot guarantee that participants will benefit directly by participating in this study; however, we are testing this platform because we believe there is a good chance that it will be helpful to participants and other users in the future.

i. There is a dearth of evidence-based digital platforms for teens that aim to decrease stress and rumination, while improving psychological well being. Therefore, if it is shown to be effective, Happify would be an accessible, low cost resource in which teens can attain mental health care early on through the reduction of perceived stress and rumination. This program would benefit teenagers themselves, but also their schools and parents, thus improving society at large.

## **VIII. FINANCIAL COMPENSATION**

**a. Financial Compensation:**

i. Parents will be entered into a raffle for a \$50 Amazon gift card for referring other parents to the prescreener via a link we send them. They

will receive one additional entry for each person they refer to the study and who reports their name and/or email. The raffle will be conducted once a month throughout recruitment, and the parent will be emailed their gift card.

- ii. Participants in both conditions will be compensated for completing the major assessments, after baseline. They will receive \$20 Tango cards for completing assessments at each point: 4 weeks (mid-point), 8 (end-point), and 12 (follow-up) weeks. If participants complete each of these assessments, they will receive \$60 total in Tango gift cards. In addition, those who complete all 3 assessments will receive a \$20 bonus, leading to a possible total compensation of \$80.
- iii. Tango cards will be delivered immediately after assessment completion through Qualtrics to the participant's preferred method of contact (phone or email). Participants receive a reward link and will be directed to the Tango Card site, where they can choose which gift card they want from 80 popular brands.
- iv. Participants will not be compensated for use of the intervention, only the completion of assessments.

## **IX. PARTICIPANTS' PRIVACY INTERESTS**

**a. Data Privacy:** The privacy of participants in this study will maintain the same privacy of regular users of Happify, which is strictly confidential, and this project's data will only be accessible to Happify researchers. All questionnaire data will be stored securely in the research coordinator's password protected-Qualtrics account, and access will be limited to the research team. Once the study is complete, data will be downloaded to the PI's secure, password-protected computer and saved using secure storage on Happify servers. In addition, when data are exported from that secure server for analysis, they will be exported in a de-identified format (without name, location, or IP address data). Data, therefore, can only be analyzed anonymously by the research team, which will help to safeguard participants' privacy interests. Any data collected about participants in the experimental condition via the Happify for Teens platform also will be stored securely using Happify servers

**b. Publication:** Data will be analyzed for internal use and publication. We intend to pursue publication of one or more papers in peer-reviewed journals and may be presenting preliminary findings at conferences. All data will be presented in aggregate form, with no identifying information attached that would reveal a participant's identity.

**c.** The research team leads who will be able to manage, access, and determine access to data are:

- i. [name] (PI, Research Scientist at Happify)
- ii. [name] (Research Associate at Happify)
- iii. [name] (Clinical Research Coordinator at Happify)

## **X. CONFIDENTIALITY AND DATA MANAGEMENT**

**a. Confidentiality:** Research data, including questionnaire data and information about participants' engagement with the Happify platform (e.g., number of activities completed during the study) will be stored securely on Happify servers and will be stored separately from any information that might be used to identify participants. Data will be contained in password-protected digital files and stored on a secure server from Happify. Only the PI and associated research staff will have access to the data files. Computers to be used by the researchers are also password-protected.

- i. Parent email and name and child email and name will be collected in the prescreener for referral and contact purposes. Child phone number will also be collected in the baseline assessment if that is their preferred method of contact for the purposes of contacting participants about the study (participants will consent to this, and contact information will be stored in a separate database).
- ii. Users will be asked to create a user ID which they will use to take the remaining assessments. This will allow us to de-identify the data but also attain participant contact information when needed. We will also obtain emails/phone numbers for contacting people regarding missed assessments and/or lack of usage. Participants who have not completed a major assessment or used Happify for 7 days will be flagged and the research coordinator of the research team will login to a secure portal to receive a report of email addresses that have been flagged. No record matching of the email addresses to contact information will be saved, and only contact information will be used for contacting purposes.
- iii. The prescreener, consenting process, and major assessments will take place outside of Happify's platform and will be administered via Qualtrics. This data will be stored securely within a password protected Qualtrics account and the password will be shared only with the Principal Investigator and other members of the research team. Prescreen data will be downloaded regularly, and this data will be downloaded to a secure, password-protected computer and then shared securely with only members of the research team who will be contacting potential participants.
- iv. Data from participants who are not eligible and do not complete the baseline assessment will be deleted from our records.

v. After the study concludes, data will be retained for our records and stored on a secure, password-protected computer and in a secure, password-protected Dropbox account, separate from research data.

### APPENDIX III.

- a. Happify Scale
- b. Perceived Stress Scale
- c. Student Life Satisfaction Scale
- d. Revised Life Orientation Test
- e. Ruminative Responses Scale Short Form
- f. UCLA Loneliness Scale
- g. PROMIS - Pediatric Sleep Disturbance Short form 4a
- h. Shortened Positive and Negative Affect Schedule for Children
- i. Baseline Assessment for Child (described in section II)
- j. Major Assessment(s) for Child (described in section II)
- k. Optional Follow-up Survey

1 INTRODUCTION

The following document outlines a statistical analysis plan (SAP) to support the analysis of data from the Happify for Teens RCT study (NCT04567888). These analyses will be used to support the writing of a manuscript and will likely lead to future conference submissions. The protocol for the RCT has been published previously (see Boucher et al., 2021). The overarching aim of this study is to test the effects of the Happify app on teens' perceived stress and rumination.

2 DATA SOURCE

The dataset consists of teen participants in the Teens RCT study. Assessment data was pulled from Qualtrics by [REDACTED], the research coordinator in charge of the Teens RCT at the time in March/April 2022. Data from each assessment were pulled separately, cleaned and then merged together in SPSS by [REDACTED], Senior Director of Research Strategy and PI on the Teens RCT. Happify usage data was pulled from Twill servers by [REDACTED] in July 2022 using user IDs and emails from RCT participants assigned to the Happify for Teens condition, and then merged with the larger dataset by [REDACTED] to prepare for the final analysis.

3 ANALYSIS OBJECTIVES

The primary objective of this study is as follows:

- Comparing the Happify for Teens condition and the waitlist control groups, examine changes in perceived stress and rumination (brooding) across baseline, 4-weeks, 8-weeks (post-intervention), and 12-weeks.

The secondary objective of this study is as follows:

- Comparing the Happify for Teens condition and the waitlist control groups, examine changes in loneliness, optimism, and sleep disturbance across baseline, 4-weeks, 8-weeks (post-intervention), and 12-weeks.

The exploratory objectives of this study are follows:

- Determine the extent to which brooding mediates the relation between treatment condition (Happify for Teens vs. control) and perceived stress.
- Among those in the Happify for Teens treatment, we will explore the extent to which app usage (i.e., number of activities completed, number of active days) associates with each of the five outcome variables from the primary and secondary objectives.

4 ANALYSIS SETS/POPULATIONS/SUBGROUPS

To be eligible for this study, the following criteria needed to be met:

- range in age from 13-17 years of age
- perceived stress scale (PSS) score greater than 14
- rumination-brooding subscale score of at least 10

We will create a subgroup of the treatment condition, stratified by those who did and did not average two activities completed per week. This threshold has been established in prior studies of the Happify app as a minimum needed for adults to benefit significantly from the program (e.g., Parks et al., 2018). We will examine descriptive statistics for these subgroups.

5 ENDPOINTS AND COVARIATES

The primary criterion of interest will be perceived stress scores, self-reported at baseline, 4-week midpoint, 8-week post, and 12-week follow-up. The secondary criterion of interest will be brooding scores at the same time points. Additionally, three exploratory outcomes will be examined at the same time points: optimism, sleep disturbance, and loneliness. The effect of the Happify treatment will be examined for each outcome.

In each model, we will covary the effects of participant age, gender, and race. Gender will be coded into two binary variables (0 = man or other, 1 = woman; 0 = woman or man, 1 = other). Race will be coded into a single binary variable (0 = White, 1 = all other races). Given that individuals who identify as White comprise almost 75% of the sample, this coding scheme prevents saturating each model with a large number of dummy codes while still preserving much of the racial distribution of the sample.

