- ii. The Qualtrics prescreener link will then be sent to the child. It includes verifying their country of residence, age, and previous Happify use. They will also complete the Perceived Stress Scale (PSS) and Ruminative Responses Scale (RRS) to ensure their scores are above thresholds (PSS  $\geq$  10; RRS  $\geq$  14). Finally, the participant must agree to study duties, including: completing the baseline assessment, completing activities via Happify through a computer or smartphone, and being contacted throughout the 12 week period by Happify research staff. Participants are told that they may be assigned to a waitlist control and will not have access to the Happify platform until the end of the study but will still have to complete assessments. They are asked to check a box if they would be willing to continue with the study and not download Happify if assigned to the waitlist. We will ask participants to agree to not discuss the study with friends or family also participating in the study. If the child meets the inclusion criteria, they will be instructed that they'll receive an email inviting them to complete the first assessment (baseline assessment) on the following Monday or Thursday (whichever comes first). They must complete this assessment in order to qualify for the study, and must continue to meet thresholds for perceived stress and rumination, and pass at least one of 7 attention checks during the baseline assessment. This email will have instructions to set up a unique study ID that will be used throughout the study to link participant data across assessments and other data collections.
- iii. In this email, participants will be provided an assent form (through Qualtrics) which is shown at the beginning of the baseline assessment. If participants choose to, they will read and agree to a statement that they will provide honest and thoughtful responses throughout the study, and a separate statement agreeing not to discuss the study with any family or friends who may also be participating in the study. Participants must complete the baseline to be randomized to condition. Participants are

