#### **e. Design and Proposed Statistical Analysis**

**I. Changes in Stress and Secondary/Exploratory Outcomes:** To assess whether changes in participants' perceived stress differed across the two groups, we plan to conduct a 2 (group: intervention vs. control) x 4 (time: baseline, 4 weeks, 8 weeks, 12 weeks) repeated-measures ANOVA on participants' PSS scores, controlling for participant age and gender. Similar analyses will be conducted on secondary and exploratory outcome measures. To determine whether usage predicted changes in these outcomes, we will also conduct regression analyses among participants in the intervention condition regressing their scores on each outcome variable onto the number of activities completed within the Happify for Teens platform, while controlling for corresponding baseline scores on that outcome.

ii. **Rumination as a Potential Mediator:** To test whether any observed changes in perceived stress can be attributed to changes in brooding, we also plan to conduct mediation analyses using Hayes' PROCESS macro for SPSS.

iii. **Data Exclusion:** Because careless responding is problematic with online surveys and may artificially increase relationships between variables, we plan to use two separate a priori mechanisms for identifying low quality data: (1) failing 3 or more attention checks in an assessment, and (2) completing an assessment at a rate faster than 1 second per item. We will then re-run the analyses described above without these participants to test whether effects differ when removing low quality data.

iv. **Happify Scale Validation:** To validate the scale for internal purposes, we will conduct confirmatory factor analysis testing the two-factor structure of the scale, and examine convergent validity by computing correlations between the positive emotion subscale and the PANAS-C-S and between the life satisfaction subscale and the SLSS that are collected at baseline.

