### III. RECRUITMENT

a. **Study Population:** This study will recruit adolescents aged 13-17 (Target  $N=800$ ) by advertising to parents on social media (e.g. Facebook, online forums, word of mouth etc...) and existing Happify users who have previously indicated they are parents of adolescents as part of the Happify onboarding process. We will also use a snowballing recruitment method, in which parents who complete the prescreener will be encouraged to share the study with others. We will continue recruiting until 800 participants have met inclusion criteria, successfully completed the baseline assessment, and have started the study.

b. **Inclusion Criteria:** Participants are those who are 13-17 years old, are located in the United States, are a new user of Happify, willing and able to complete the study activities, agree to potentially being selected for the waitlist comparison, agree to not discuss the study with friends or family, report elevated levels of perceived stress (PSS score of at least 14) and rumination (RRS-Brooding score of at least 10), and have a

parent who is willing to consent to the study. Participants are required to complete and pass the baseline assessment to be included in this study.

**c. Exclusion Criteria:** Participants may withdraw from the study or skip assessments at any time; however during the prescreening and/or baseline process, potential participants will be disqualified if they indicate:

- i. They are not 13-17 years old.
- ii. They reside outside of the United States
- iii. They have previously registered for or used Happify
- iv. They are not willing and able to complete the study activities
- v. They indicate that they are not willing to continue the study or refrain from downloading Happify if selected to be on the waitlist
- vi. They are not willing to use a mobile app or internet website
- vii. They do not agree to refraining from discussing the study with friends or family
- viii. They have a PSS score of below 14
- ix. They have an RRS-Brooding score of less than 10
- x. They do not agree to be contacted
- xi. Their parent does not consent to the study
- xii. Participants will also be excluded if they do not complete the baseline assessment, or if they do but fail at least 7/7 attention checks.

2. **Sample Size:** We will recruit 800 participants to be in this study, 400 in each condition.

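### The SAP plans no use of the prescreen PSS score that every randomised teen should have; adding it to a baseline-adjusted model is a small, cheap gain in precision

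*SAP*

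**What the plan says.** Protocol II.a (Study Design) gives the sequence. Children first answer a prescreener: "They will also complete the Perceived Stress Scale (PSS) and Ruminative Responses Scale (RRS) to ensure their scores are above thresholds". The baseline survey is offered on the next Monday or Thursday, and there they "must continue to meet thresholds for perceived stress and rumination". Allocation comes last: "Participants must complete the baseline to be randomized to condition". Protocol II.a and X.a order deletion of records for teens who do not qualify or do not finish baseline. Protocol X.a also states: "Prescreen data will be downloaded regularly".

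For the analysis, Protocol II.e plans a repeated-measures ANOVA "controlling for participant age and gender". SAP 5 says: "In each model, we will covary the effects of participant age, gender, and race". It treats baseline PSS as one of four outcome occasions. The equation in SAP 7.2 contains condition and time, with no product term and no pre-randomisation score as a covariate. SAP 6 adds that the final models will carry auxiliary variables as covariates, found by correlating demographics and other variables in the dataset with missingness. SAP 2 describes merging assessment and usage data and does not mention the prescreener.

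On sample size, Protocol III says: "We will recruit 800 participants to be in this study, 400 in each condition". No effect size, SD, power or correlation accompanies it.

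**The concern.** A stress score taken shortly before baseline should predict later stress. A single self-report baseline is noisy, and selection at an entry cut-off narrows its range, so a second pre-randomisation score can add information. Because it precedes allocation, adjusting for it does not bias the randomised comparison. Leaving it out makes the standard errors for stress, and possibly brooding, somewhat larger than they need to be, in a trial where SAP 7.2 speaks of relatively high attrition. What is at stake is efficiency, not validity. Optimism, sleep disturbance and loneliness have no prescreen score and are not affected.

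**Working it through.** **Inputs.** From Protocol III: 800 participants, 400 per arm. The documents give no alpha, power, effect size, SD or correlation, so 800 cannot be reproduced and every correlation below is assumed.

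**Step 1: gain beyond a baseline score that is already adjusted for.** Take PSS with unit SD. Let rb and rs be the correlations of the follow-up score with baseline and prescreen, and r the correlation between those two.

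- Baseline only: residual variance = 1 − rb².
- Baseline and prescreen: 1 − (rb² + rs² − 2·rb·rs·r)/(1 − r²). When rb = rs = ρ this is 1 − 2ρ²/(1 + r).

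Example, ρ = 0.5 and r = 0.7: 1 − 0.25 = 0.750, and 1 − 0.5/1.7 = 0.706. The ratio is 0.941, and 800/0.941 ≈ 850.

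| rb | rs | r | Baseline only | Plus prescreen | Ratio | 800 acts like |
|---|---|---|---|---|---|---|
| 0.3 | 0.3 | 0.3 | 0.910 | 0.862 | 0.947 | 845 |
| 0.5 | 0.5 | 0.5 | 0.750 | 0.667 | 0.889 | 900 |
| 0.7 | 0.7 | 0.7 | 0.510 | 0.424 | 0.830 | 963 |
| 0.5 | 0.5 | 0.7 | 0.750 | 0.706 | 0.941 | 850 |
| 0.5 | 0.5 | 0.8 | 0.750 | 0.722 | 0.963 | 831 |
| 0.5 | 0.45 | 0.8 | 0.750 | 0.743 | 0.991 | 807 |
| 0.5 | 0.4 | 0.8 | 0.750 | 0.750 | 1.000 | 800 |

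The two scores are planned only days apart, so r is probably high. That favours the lower rows, where the gain is 0% to 6%.

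**Step 2: selection at both screens.** All of these are simulations on assumed values.

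- SD 6.5, reliability 0.6–0.8, both scores at least 14: ratio 0.92–0.99, a gain of 1–8%. Since 800/0.99 ≈ 808 and 800/0.92 ≈ 870, this is worth about 10 to 70 participants.
- The same selection, with true pre-randomisation and week-8 stress correlated 0.6–1.0: ratio 0.82–0.98.
- Mean 18–22, SD 6, cut at 14, correlations set directly: ratio 0.91–0.95.

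**Step 3: dependence on how baseline is handled.** In a condition-by-time model with baseline as a free outcome, the week-8 contrast is a difference in change, with variance 2(1 − rb), or 1.0 at rb = 0.5.

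- Prescreen as a main effect only: the variance stays at 1.0, because the same shift applies at every visit and cancels.
- Prescreen with its time interaction: variance 2(1 − rb) − (rs − r)². In simulation with both scores at least 14 (mean 18–22, SD 6.5, reliability 0.6–0.8), the ratio is 0.95–1.00, a gain of 0–5%. Without selection it can be larger: at rb = rs = 0.5 and r = 0.8 it is 1.0 − 0.09 = 0.91. That is still worse than baseline adjustment alone (0.75).
- Baseline adjusted for, all correlations 0.5: 1.0 falls to 0.750, and prescreen then takes it to 0.667. With true-score correlation 0.6–0.8 and selection, baseline adjustment alone gives a ratio of 0.74–0.87.
- In the most favourable case for prescreen, all correlations 0.7, the steps are 0.60 to 0.51 to 0.424, so the two are of similar size.

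**Step 4: power, for scale.** With an assumed difference of 0.20 SD, two-sided 0.05 and 400 complete per arm, baseline adjustment at rb = 0.5 gives 90.4%. Adding prescreen gives 91.4% (rs = 0.5, r = 0.8) or 93.4% (all 0.5).

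**The case against.** Several points on the other side stand.

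- **SAP 6 leaves a door open.** It would be wrong to say the SAP adjusts only for demographics. Prescreen scores could enter as auxiliary variables, but only if they were merged and happened to correlate with missingness. Their use is neither planned nor excluded.
- **Baseline handling is the larger lever**, and it needs no linkage. The prescreen gain is small without it.
- **Linkage is not free.** The study ID is created after the prescreener. A parent's email may stand in for the child's, and several children in a family may enrol (Protocol II.a). Analysis exports are de-identified (Protocol IX) and identifiers are stored separately (Protocol X). Retention of eligible teens' prescreen scores is inferred from the deletion rules, not stated.

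Two stronger readings are tempting and not supported.

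- **A large loss of precision.** A reader might take it from the SAP 7.2 equation. Under equal correlations ρ, the Condition coefficient's variance factor is (1 + 3ρ)/4, and a prescreen covariate subtracts ρ². At ρ = 0.5 that is 0.625 falling to 0.375, a ratio of 0.600. But this coefficient averages over four occasions including baseline, so it dilutes a constant post-baseline effect to 0.75 of its size, and it does not estimate the between-group change that SAP 3 sets as the objective. The apparent gain arises mainly because that equation has no pre-randomisation score as a covariate.
- **A second brooding score certainly exists.** Protocol II.a names the RRS in the prescreener, with cut-offs of PSS 10 and RRS 14. Protocol III names RRS-Brooding, with PSS 14 and brooding 10. SAP 4 asks for PSS above 14. That the prescreen measure is the brooding subscale is plausible but not established.

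**Conclusion.** The point holds as a minor efficiency matter. Each randomised teen should have a prescreen PSS score that precedes allocation, and no planned analysis names it. Beyond a properly used baseline score, it would cut the treatment-effect variance by roughly 1–8%, or 0–18% over wider assumptions. If baseline remains a free outcome in a condition-by-time model, the cut is about 0–5%. In most of the cases examined, the greater part of the available gain comes from baseline adjustment. All sizes rest on assumed reliabilities, correlations and an assumed cut-off of 14 at both screens, none of which the documents settle. The omission biases nothing.

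**What to change.** In SAP 5 and 7.2, for the post-baseline treatment comparison on PSS:

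1. Adjust for baseline PSS, either as a covariate with its interaction with time or by constraining baseline means to be equal across arms.
2. Add prescreen PSS and its interaction with time.
3. Do the same for brooding if the prescreen measure is confirmed to be the brooding subscale.
4. Amend SAP 2 to say whether prescreen data are linked. SAP 2 describes the data as already pulled, so record the choice before any between-arm result is examined.

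The entry thresholds and the name of the rumination measure differ between Protocol II.a, Protocol III and SAP 4. These passages must be reconciled.

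The cost is a one-time linkage by name or email, confirmation that eligible teens' prescreen scores were kept, and a check that parental consent and teen assent cover their use. No new data are needed. If linkage proves impracticable, step 1 alone still brings most of the benefit in most of the cases examined.
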